## List of Abbreviations and Terms

ADE	Adverse Device Effect
AE	Adverse Event
AUC	Area under the curve
CC	Analysis of images obtained by cCeLL
eCRF	Electronic Case Report Form
DD	Device Deficiency
FAS	Full Analysis Set
FS	Frozen section analysis
GCP	Good Clinical Practice
ICF	Informed Consent Form
ISO	International Organization for Standardization
ITT	Intent-To-Treat
LOCF	Last Observation Carried Forward
MAST	Multiple Allergen Simultaneous Test
PBS	Phosphate Buffered Saline
PP	Per Protocol
PS	Permanent section analysis
REB	Research Ethics Board
SAE	Serious Adverse Event
SADE	Serious Adverse Device Effect
SOC	System Organ Class
SOP	Standard Operating Procedure
UADE	Unexpected Adverse Device Effect

## 1. Study Title

A prospective, multi-centered, assessor-blinded clinical performance study to assess the sensitivity and specificity of the proposed cell/tissue histopathology image processor cCeLL – Ex vivo (Confocal Fluorescence Endomicroscopy) in diagnostic yield during brain tumor surgery

## 3. Background and Purpose of the Investigation

### 3.1 Study Objective

The purpose of this clinical study is to confirm sensitivity and specificity of the cCeLL – Ex vivo in intraoperative brain tumor diagnosis as compared to analysis with frozen section.

### 3.2 Background

Cancer is a leading cause of death, accounting for nearly 1 out of 6 death worldwide (Ferlay et al., 2020; de Martel et al., 2020; WHO, 2020).

[figure not shown]
The existing workflow for intraoperative brain tumor diagnosis involves tissue biopsy, processing, analysis and confirmation by a pathologist using frozen section, and relaying the result back to the surgeon. The current intraoperative diagnosis based on frozen section analysis is time-, resource-, and labor-intensive. The process takes over 40 minutes on average but may

take longer if biopsied specimen is insufficient or requires repeated analysis. Thereby the development of an efficient device that allows intraoperative real-time diagnosis is enforced.

Confocal Laser Endomicroscopy is a promising diagnostic tool to replace current standard ‘frozen section analysis’ by allowing intraoperative real-time high-resolution visualization of tissue of interest. Confocal Fluorescence Endomicroscopy follows the general principles of fluorescence, which is the characteristic of fluorescence-stained specimen (‘tissue’) that absorb light of short-wavelength and emits light of long-wavelength. This medical device visualizes the intensity of light emitted from a specimen which varies according to the specimen’s degree of light absorbance (White et al., 1987; Amos and White, 2003).

When the probe of the device, which contains optical fibers, is placed in contact with the specimen or close to within several hundred  $\mu\text{m}$  of the specimen, the optical signal generated from the main body gets transmitted to the specimen through the probe and then absorbed by the specimen. The specimen then gets activated and emits fluorescent light, and this fluorescent light returns to the main body of the device through the optical fibers of the probe. The mechanism behind optical fibers is that light incident at a specific angle proceeds to total reflection due to the inside and outside of the optical fibers each being made with differing densities and refractive indices. The optical signal which returned to the main body through the optical fibers is detected as an electronic signal by the photodetector in the main body. The electric signal is then converted to a digital signal by the converter inside the main body of the device, and the digital signal is then processed by the PC through its software and exported as an image onto the monitor.

Several global medical device companies have developed promising digital-biopsy devices based on confocal microscopy for past few years and commercialized micro-probe-based optical fusion imaging devices that can be placed in contact with the patient's organs directly. However, technological barrier in micro-miniaturization of probe still exist as seen in marketed devices, which limits its use in various human organ systems. These limitations are observed as the probe being too large for intraoperative use (Vivascope, USA) (Mavig GmbH, 2019), limited number of optic fiber bundles leading to inadequate resolution of images for pathologic diagnosis (Cellvizio, France) (Mauna Kea Technologies, 2021), or difficulty in compensating body movements for respiratory/circulatory activities due to limited laser scanning speed of the probe (Convivo, Germany) (Carl Zeiss Meditec AG, 2019). The proposed investigational device designed with an innovative optic probe and image-processing technology to enable detection and capture of high-resolution images whilst in operating room.

### Anticipated Economic/Industrial Impact and Advancement – Establishment of Digital Histopathology System

- ① cCeLL – Ex vivo allows rapid scanning, capturing, and storing of high-resolution images of biopsy specimen, without undergoing lengthy standard procedure, as a complete Digital Histopathology System. Hospitals are suffering from the increased burden in storing pathology tissue slides, hence in process of converting originals into digital slides and storing into digital image repository.
- ② cCeLL – Ex vivo enables capturing of digital images without producing physical tissue slides, which is a labor-, time- and cost-intensive process, as well potentially reduces carbon emission. As the digital images created by cCeLL – Ex vivo are saved as electronic files without requiring utilization of separate viewer system, it allows efficient data management and accelerates conversion rate and smooth adaptation into digital histopathology system.

[figure not shown]
## 4. Investigational Device

[figure not shown]
### 4.1 Device Standard

Item	Specification		
Electrical Specification	Maximum power consumption at the maximum output	300VA	
	Electrical rating input	100-240VAC, 50/60Hz	
	Protection degree for electric shock	Class 1 equipment	
Performance specification	Laser	Output wavelength	1. CX100-2W2C488775: 480- 492 nm, 770- 785 nm 2. CX100-1W1C488: 480-492 nm 3. CX100-1W1C785: 770 -785 nm
		Laser Class	3R
	Imaging	Output power	1. CX100-2W2C488775 a. 488 nm: max. 2.5 mW b. 775 nm: max. 3.5 mW 2. CX100-1W1C488: max. 2.5 mW 3. CX100-1W1C785: max. 3.5 mW
		Operation mode	Continuous mode
		Laser medium	Laser diode (semiconductor)
Storage and Maintenance	In-Use	Field-of-View (FOV)	500μm(±10%) x 500μm(±10%)
		Frame count per second	2 - 10fps
	Storage	Temperature	15°C - 35°C
		Humidity	30% - 75%

#### 4.2 Appearance of the Device

Item	Description
Main device	
Probe	

### 4.3 Operating Mechanism

The investigational medical device visualizes cells of a biological specimen which has been resected from the body and to which dye has been applied by measuring the intensity of the fluorescence signal that is generated by shooting a laser onto the specimen. The device is capable of capturing images of regions several  $\mu\text{m}$  wide of a specimen at depth of several hundreds of  $\mu\text{m}$ , and visualizing them in 2D through its complementary software. Confocal Fluorescence Endomicroscopy follows the general principles of fluorescence. Fluorescence refers to a phenomenon in which a fluorescent object emits light of long wavelength by absorbing light of short wavelength. This device visualizes the intensity of light emitted from a specimen which varies according to the specimen's degree of light absorbance.

When its probe, which contains optical fibers, is placed in contact with the specimen or close to within several to several hundred  $\mu\text{m}$  of the specimen, the optical signal generated from the main body gets transmitted to the specimen through the probe and then absorbed by the specimen. The specimen then is activated and emits fluorescent light. This fluorescent light returns to the main body of the device through the optical fibers of the probe. The mechanism behind optical fibers is that light incident at a specific angle proceeds to total reflection due to the inside and outside of the optical fibers each being made with differing densities and refractive indices. The optical signal which returned to the main body through the optical fibers is detected as an electronic signal by the photodetector in the main body. The electric signal is then converted to a digital signal by the converter inside the main body of the device, and the digital signal is then processed by the PC through its software and exported as an image onto the monitor.

#### **4.4 Intended Use**

This investigational medical device is a diagnostic tool that aims to provide rapid and precise intraoperative assessment of biopsied neoplastic tissue specimen from a brain tumor. By enabling the fluorescence staining, visualizing, capturing and storing image data while in the operation room, standard time-consuming and labor-intensive preparation of specimen sectioning may not be necessary.

#### **4.5 Target Health Condition**

Benign/Malignant Brain Tumor

#### **4.6 Device Accountability**

##### **4.6.1 Labeling**

The investigational medical device will be labelled according to the requirements of ICH-GCP, ISO 14155, and all other applicable regulatory guidelines. The device label will contain the following information in required official languages (i.e. English and French in Canada; Korean in Korea):

- a. Name of the device
- b. Name and address of manufacturer
- c. Identifier of the device
- d. Package content
- e. Expiry date
- f. Specification (as necessary for proper use)
- g. Directions for use
- h. Warning and cautions
- i. Contraindications
- j. Storage condition

All investigational devices used in Canada will be labelled “Investigational Device” and “To be Used by Qualified Investigators Only” and “Instrument de recherche” and “Réservé uniquement à l’usage de chercheurs compétents” accordingly to Health Canada regulations.

##### **4.6.2 Maintenance, Handling, and Record Keeping**

The investigational medical device will be provided by Sponsor only after obtaining written approval/authorization from the REB and regulatory authorities. Access to investigational devices shall be controlled and the investigational devices shall be used only in the clinical investigation and according to the study plan. Device accountability will be maintained and will document the physical location of all investigational devices from shipment of investigational devices to the investigation sites until return or disposal. The Sponsor must document and retain all records related to device manufacture, shipping, receipt, return, or disposition. The investigator/investigator’s designee will acknowledge receipt upon reception.

Sponsor or Sponsor's designee must identify and document the SOP procedures for the return of investigational device upon study completion or in case of issue related to device.

The Sponsor or manufacturer must not provide or dispense any parts of investigational medical device to any other study site or investigator. The device must not be used other than for the intended use specified in the trial protocol.

#### **4.6.3 Receiving, Storage, and Return**

Device accountability will be maintained and will document the physical location of all investigational devices from shipment of investigational devices to the investigation sites until return or disposal. The principal investigator or an authorized designee shall keep records documenting the following:

- a. name(s) of person(s) who received, used, returned, or disposed of the device;
- b. the date of receipt, identification, and quantity of each investigational device (lot number);
- c. the expiry date, if applicable;
- d. the date or dates of use;
- e. the date on which the investigational device was returned;
- f. the date of return of unused, expired, or malfunctioning investigational devices, if applicable.

A site monitor will review the inventory and accountability log during site visits and at the completion of the study. If the study is completed, prematurely terminated, or suspended, the Sponsor shall promptly inform the investigators, the REB, the regulatory authorities of the reason for termination or suspension, as specified by the applicable regulatory requirements; and the investigational medical device will be return to the Sponsor or alternative disposition of used/unused products as per request by the Sponsor. The investigational medical device is intended for use by qualified investigators only.

## **5. Inclusion and Exclusion Criteria and Sample Size Determination**

### **5.1 Inclusion Criteria**

The biological specimens (hereafter referred to as ‘tissue’) and/or images to be used in this trial must be collected from patients who satisfy all of the following inclusion criteria:

1. Male or female patients  $\geq$  19 years of age.
2. Patient is suspected to have a brain tumor and has been scheduled for neurosurgery with a potential tumor resection.
3. Patient is willing and able to provide informed consent and understand its content.

### **5.2 Exclusion Criteria**

Tissue and/or images to be used in this trial must be collected from patients who do not meet any of the following exclusion criteria:

1. Patient has undergone several surgeries on lesion of interest.

### **5.3 Tissue Eligibility**

Eligible tissue will meet all of the following:

1. Tissue from an eligible and consented patient at a participating site
2. Any normal tissue obtained from inevitable resection during standard surgery

### **5.4 Sample Size**

The sample size refers to the number of analyzable tissue samples collected from participants. There may be multiple samples collected from each participant.

There will be 250 analyzable tissue samples required (200 tumor positive and 50 normal) for this study.

#### **5.4.1 Number of Specimens**

A total of 250 analyzable samples (200 samples for cancer, 50 samples for normal) are required.

- Korea University Anam Hospital: 36 samples (cancer: 30 samples, normal: 6 samples)
- Seoul National University Hospital: 57 samples (cancer: 50 samples, normal: 7 samples)
- Samsung Medical Center: 57 samples (cancer: 50 samples, normal: 7 samples)
- St.Michael’s Hospital, Unity Health: 100 samples collected from a total of 65 participants (cancer: 70 samples, normal: 30 samples)

With an expected dropout rate of 30%, the number of samples to be collected is 358 samples (286 cancer samples, 72 normal samples)

- Korea University Anam Hospital: 51 samples (cancer: 42 samples, normal: 9 samples)
- Seoul National University Hospital: 82 samples (cancer: 72 samples, normal: 10 samples)
- Samsung Medical Center: 82 samples (cancer: 72 samples, normal: 10 samples)
- St.Michael's Hospital, Unity Health: 143 samples collected from a total of 50 participants (cancer: 100 samples, normal: 43 samples)

## 5.5 Study Duration

It is expected that the study will run for about 18 months in total from the time the study sites are activated. Enrollment is expected to 8 months in Korea and up to 12 months in Canada. There will be additional time for data collection, data cleaning and analysis.

[figure not shown]
# 6. Study Procedures

## 6.1 Study Design

Prospective, multi-center, assessor-blinded clinical study. Samples will be paired and compared against the current standard of assessment.

## 6.2 Study Assessments and Procedures

There will be up to three (3) tissue sample types assessed for each participant: 1- center-of-tumor, 2- normal tissue (collected from inevitable standard resection), and 3- margin tissue. Depending on each participant's circumstance, the number of sample tissues harvested will differ from minimum of one to maximum of three. All tissue samples will be assessed with the investigative device and compared against frozen section analysis.

1. Samples will be collected from consented participants who have satisfied the eligibility criteria.
2. Tissues will be removed as part of the standard neurosurgical procedure. Normal tissues obtained from inevitable resection during the course of surgery.
3. Collected samples will be processed as follows:
  1. Wash the biopsied tissue with Phosphate Buffered Saline (PBS)
  2. Place the tissue on a glass slide
  3. Apply dye onto the tissue
  4. After 1 minute, wipe on gauze and then scan (i.e., cCeLL imaging) the tissue using Pixecton (probe) connected to cCeLL – Ex vivo
  5. Send the processed tissue to pathology to obtain images in the form for frozen sections analysis (FS)/permanent sections analysis (PS)
4. Image recordings of sample tissue using cCeLL – Ex vivo are taken and the obtained data is stored (CC).
5. cCeLL – Ex vivo image data of the collected samples is sent to the central core.
6. The result of frozen section analysis (FS) will be collected from the pathology department of each site.
7. The result of permanent section analysis (PS) of corresponding paraffin-embedded tissue section (PS) will be collected from the pathology department of each site. PS will serve as a reference standard to the analysis result of CC and FS.
8. An interpreting pathologist will analyze given images (CC) and is not allowed to review the reference standards (PS).
9. The cCeLL – Ex vivo image data will be de-identified such that only the unique reference numbers will be displayed in the images provided, and participant information including participant enrollment number and surgery information will be removed.
10. The types of the images obtained from this procedure are as follows:

cCeLL – Ex vivo will capture image data of a resected tissue, prior to frozen sectioning (FS) and permanent sectioning (PS). The sample is used to evaluate the presence or absence of tumors, and also to evaluate the tumor types.

Method of analysis	Image data	Reference standard	Result of analysis by a pathologist 1
cCeLL – Ex vivo	CC	PS	CC-H
Permanent section	PS	PS	
Frozen Section	FS	PS	

**CC** : Analysis of images obtained by cCeLL

**FS** : Frozen section analysis

**PS** : Permanent section analysis

**H** : Pathologist

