	
2) Tissue will be removed as part of the standard neurosurgical procedure. Normal tissue obtained from inevitable resection during the course of surgery. There will be no deviation from normal surgical practice to acquire tissue samples.
 
3) Image recordings of sample tissue using cCeLL – Ex vivo are taken and the obtained data is stored (CC).
 
4) cCeLL – Ex vivo image data of the collected samples is sent to the central core.
 
5) The result of frozen section analysis (FS) will be collected from the pathology department of each site.
 
6) The result of permanent section analysis (PS) of corresponding paraffin-embedded tissue section (PS) will be collected from the pathology department of each site. PS will serve as a reference standard to the analysis result of CC and FS.
 
7) An interpreting pathologist will analyze given images (CC-H) and is not allowed to review the reference standards (PS) until all interpretations have been completed.
 
8) The cCeLL – Ex vivo image data will be anonymized such that only the unique reference numbers will be displayed in the images provided, and participant information including participant enrollment number and surgery information will be removed.
 
9) The types of the images obtained from this procedure are as follows:
 
cCeLL – Ex vivo will capture image data of a resected tissue, prior to frozen sectioning (FS) and permanent sectioning (PS). The biopsied samples can be used to evaluate the presence of tumors, and the tumor types.
 

Method of analysis	Image data	Reference standard	Result of analysis by a pathologist	

cCeLL – Ex vivo	CC	PS	CC-H	

Permanent section	PS	PS		

Frozen Section	FS	PS		

 
CC : Analysis of images obtained by cCeLL FS : Frozen section analysis PS : Permanent section analysis H : Pathologist
 
10) Data will be analyzed by a statistician. Sensitivity and specificity will be calculated as follows:
	Method of analysis	Image data	Reference standard	Result of analysis by a pathologist	cCeLL – Ex vivo	CC	PS	CC-H	Permanent section	PS	PS		Frozen Section	FS	PS	
Method of analysis	Image data	Reference standard	Result of analysis by a pathologist														
cCeLL – Ex vivo	CC	PS	CC-H														

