#### **6.7 Assessment Data**

Test results will be collected and compared from all three (3) modalities (cCell, FS, PS). Blinded assessments of cCell images will be documented from the site pathologist for each analyzable image.

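### No rule masks the permanent-section reference read to the frozen-section result, so any carry-over of frozen-section errors biases the sensitivity and specificity comparisons against cCeLL

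*Combined protocol and SAP*

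**What the plan says.** Section 6.2, item 6, gives the source of the comparator: "The result of frozen section analysis (FS) will be collected from the pathology department of each site". Item 7 gives PS the same source and its role: "PS will serve as a reference standard to the analysis result of CC and FS". The Synopsis (Study Procedure) repeats both.

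The masking rule points one way. In the Synopsis the pathologist who interprets the cCeLL images "is not allowed to review the reference standards (PS) until all interpretations have been completed", and item 8 of section 6.2 has the same rule without the time limit. Section 6.7 applies the word blinded to the cCeLL reading alone: "Blinded assessments of cCell images will be documented from the site pathologist for each analyzable image". Section 6.1 calls the trial "Prospective, multi-center, assessor-blinded clinical study" but does not say that the assessor includes whoever reads PS. Section 6.3 has blinding in its title but contains only numbering rules.

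Section 8.1 makes agreement, sensitivity and specificity the primary endpoints. Section 8.3.1 compares FS and cCeLL sensitivity (5-point margin) and specificity (10-point margin) for non-inferiority, with PS as truth. Section 5.4 sets the numbers: "There will be 250 analyzable tissue samples required (200 tumor positive and 50 normal) for this study".

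**The concern.** A reference read with one index test in view can inherit that test's errors. Here that index test is the comparator. Carry-over therefore shifts the FS-minus-cCeLL difference itself, and not only the absolute accuracy of each method.

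The sample split makes specificity the more exposed endpoint. FS at 90% misses 20 of 200 tumors but miscalls only 5 of 50 normals. Each missed tumor that PS also calls negative enters the small tumor-negative group, where FS is scored right and a correct cCeLL call is scored wrong. The bias favors FS, so the main risk is that a device truly as good as FS fails to show it.

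**Working it through.** **Inputs from the plan.** 200 tumor and 50 normal samples (section 5.4). Anticipated sensitivity and specificity of 90% for both methods, margins of 5 and 10 points, and pilot agreement above 86% (section 8.3.1). The bound in 8.3.1 is FS minus cCeLL plus z·√(discordant pairs)/n. The text calls it a 97.5% bound, while the formula prints z with subscript 0.05, so both z = 1.96 and z = 1.645 were run.

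**Assumptions not in the plan.** PS is correct except that it repeats a share q of FS errors, in both directions. cCeLL is also wrong in a share w of FS errors. With both methods at 90%, agreement = 1 − 2 × 0.10 × (1 − w) = 0.80 + 0.20w. So 86% agreement means w = 0.3, 90% means w = 0.5, and independent errors (w = 0.1) mean 82%.

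**The plan's own figures.** With an unbiased reference, the chance that the estimated specificity difference stays below 10 points with 50 samples is 92-98% for discordance of 14-20% (plan: above 80%). For sensitivity it is 93-98% (plan: above 90%). For agreement, the chance of an estimate above 80% is 99.4% (plan: above 90%). All three statements hold as inequalities.

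**Worked case, q = 20%, w = 0.3.** PS turns 4 of the 20 missed tumors negative and 1 of the 5 false positives positive.

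- PS-negative samples: 50 + 4 − 1 = 53
- FS specificity: (45 + 4)/53 = 92.5%
- cCeLL specificity: (45 − 0.7 + 1.2)/53 = 45.5/53 = 85.8%
- Gap: 3.5/53 = 6.6 points, where the true gap is 0
- Sensitivity: FS 181/197 = 91.9%; cCeLL (180 − 2.8 + 0.3)/197 = 90.1%; gap 1.8 points

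**General form.** Specificity gap = 25q(1 − w)/(50 + 15q). Sensitivity gap = 25q(1 − w)/(200 − 15q).

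Apparent specificity gap, in points:

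| Carry-over q | 90% agreement | 86% agreement | 82% agreement (independent errors) |
|---|---|---|---|
| 5% | 1.2 | 1.7 | 2.2 |
| 10% | 2.4 | 3.4 | 4.4 |
| 20% | 4.7 | 6.6 | 8.5 |

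At q = 20% the sensitivity gap is 1.3, 1.8 and 2.3 points in the same three columns, against a 5-point margin.

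**Chance of passing specificity non-inferiority at 86% agreement.** This is the exact multinomial sum over discordant counts using the plan's bound, with PS-negative n rounded to 50, 51, 52 and 53.

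| Carry-over q | z = 1.96 | z = 1.645 |
|---|---|---|
| 0 | 52% | 62% |
| 5% | 38% | 47% |
| 10% | 26% | 34% |
| 20% | 11% | 18% |

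At 90% agreement and q = 20% the chance is 23% (z = 1.96) or 35% (z = 1.645).

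**The case against.** The strongest reply is that the plan nowhere says the PS pathologist sees the FS result, and that no carry-over rate can be found in it. Both statements are true. What the documents show is the lack of a rule, in a setting where both results come from one department. The gap is nearly proportional to the assumed share, so the tables are illustrations and not forecasts.

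A reader might infer four stronger things that the documents do not support.

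- **A specificity gap of 7 to 8 points is to be expected.** That needs 20% carry-over and, for 7.5 to 8.5 points, agreement of 84% down to 82%. Section 8.3.1 reports pilot agreement above 86%, which puts the 20% case at 6.6 points or less. Independent errors are not excluded, because the same section treats an 80% null as compatible with 90% accuracy, so 8.5 stays as an outer case. Fixing the 200/50 split by PS instead of true status moves the 86% figure only from 6.6 to 7.0.
- **PS is also exposed to the cCeLL images.** Section 6.2, item 5, sends the images to a central core, and no step gives them to the PS reader. The route is only a possibility, because section 6.7 names the site pathologist as cCeLL reader. Such carry-over would favor the device.
- **The low chance of passing specificity is a masking problem.** With no carry-over it is already 52% or 62% at 86% agreement. That is a separate sample-size issue, and only the fall from there belongs to this point.
- **All primary endpoints are affected.** Agreement compares FS with cCeLL directly and does not use PS.

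**Conclusion.** The point stands as a gap in masking. No section masks the PS read to FS, requires different readers for the two, or provides for an independent PS read, and PS is the truth for two of the three primary comparisons. The direction follows from the design: carry-over from FS favors FS and works against cCeLL.

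The size is conditional on an assumed carry-over share and on a PS that is otherwise correct. With agreement of 86% to 90%, the specificity comparison shifts by 1.2-1.7 points at 5% carry-over and by 4.7-6.6 points at 20%. Even 5% lowers the chance of passing at 86% agreement by 14 to 15 percentage points (52% to 38%, or 62% to 47%). The effect on sensitivity is smaller relative to its margin. The change is worth making because it is cheap, and because an unmasked PS call cannot be made masked afterwards.

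**What to change.** In section 6.2, item 7:

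- Have the pathologist who signs out PS record a sample-level tumor/not-tumor call on the PS slide before opening the FS report or any cCeLL image. Make that call the study's reference standard. Routine sign-out then proceeds unchanged.
- Present the slide for that call under a neutral code. The specimen numbers in section 6.3.1 carry a classification letter (C, P or N) that may reveal the sample class.
- Record in the eCRF whether the same person read FS and PS. Where the rota allows, use a different pathologist already in the department for PS. A closed report does not mask someone who made the frozen call.
- Add a sensitivity analysis of sensitivity and specificity limited to samples with different FS and PS readers.
- State that the cCeLL reader of a sample does not sign out its PS.

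The cost is a short extra step at sign-out, two eCRF fields, the neutral coding, and a protocol amendment with the approvals that section 9.1 requires if it counts as substantial. Masking stays incomplete where one person read both FS and PS; the eCRF field makes those samples identifiable.

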	
ii. The cCeLL-Ex vivo reading time by the pathologist is measured and recorded in minutes from the time of capturing the cCeLL-Ex vivo image of each brain tumor to the time of the final reading.
 
iii. The imaging and reading time for frozen section is measured in minutes from the time of resecting the specimen undergoing frozen section in the operating room to the time when the pathology department of each institution obtains a frozen section image and reports the findings.
 
iv. Format: _____ Hours _____ Minutes
 
2. Comparison of cCeLL accuracy of evaluating the tumor types via Ex-vivo imaging with the accuracy using frozen section
 

i. Evaluation of tumor types via cCeLL-Ex vivo images by 1 pathologist : Agreement between the result of CC-H and the result of PS

ii. Evaluation of tumor types via frozen section: Agreement between the result of FS and the result of PS

 
3. cCeLL – Time and number of images required to diagnose Ex vivo imaging
 

i. The number of images required for the pathologist to read the brain tumor cCeLL – Ex vivo image will be measured and averaged.

ii. cCeLL – Ex vivo reading time uses that of secondary endpoint 1.

iii. *Average number of images required for cCeLL – Ex vivo image reading of 1 brain tumor specimen: _____

 
4. Non-diagnostic image
 

i. The total number of cCeLL Ex-vivo images among the images confirmed in the vivo reading, and the proportion of the number of images that cannot be read are stated as a percentage (%).

ii. The number of images that cannot be read is recorded when the reader reads it.

 
5. AUC value
 

i. Based on the results of each endpoint, the sensitivity and false positive rate (1-specificity) are used to draw the ROC (Receiver Operating Characteristic) Curve to evaluate the performance of the diagnosis to distinguish between positive and negative, and the accuracy of the diagnosis is evaluated through the AUC (Area Under the Curve) value obtained from the area below the ROC curve.

--	--

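### The explicit viewing ban on the cCeLL reader names only the permanent section; it should also cover frozen section, the comparator in all three primary tests

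*Combined protocol and SAP*

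**What the plan says.** Section 6.1 gives the design as "Prospective, multi-center, assessor-blinded clinical study", and the protocol title uses the same term. Section 6.7 calls the cCeLL assessments blinded and attributes them to the site pathologist, directly after a sentence listing cCeLL, FS and the permanent section (PS) as the three modalities to be compared. None of these places says what the assessor is blinded to.

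The explicit rule appears twice. Section 6.2 item 8 says: "An interpreting pathologist will analyze given images (CC) and is not allowed to review the reference standards (PS". The Synopsis (Study Procedure, item 7) says that the reader "is not allowed to review the reference standards (PS) until all interpretations have been completed". Both name PS only. Section 6.2 item 7 makes PS the reference standard for cCeLL and for FS alike, and Section 6.3.2 numbers FS under its own heading, so FS is not covered by the term used in the ban.

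On timing, Section 6.2 says that the device "will capture image data of a resected tissue, prior to frozen sectioning (FS) and permanent sectioning (PS". The Synopsis measures the cCeLL reading time "from the time of capturing the cCeLL-Ex vivo image of each brain tumor to the time of the final reading", with no latest time. The FS clock runs to "the time when the pathology department of each institution obtains a frozen section image and reports the findings". On who holds FS, Section 6.2 item 6 says: "The result of frozen section analysis (FS) will be collected from the pathology department of each site".

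Two further provisions bear on exposure. Item 5 of Section 6.2 sends the images to a central core, and item 9 strips participant and surgery information so that only a unique reference number is displayed.

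**The concern.** Section 8.1 makes three quantities primary: agreement between cCeLL and FS, sensitivity, and specificity. Section 8.3.1 tests agreement against 80%, and tests sensitivity and specificity as non-inferiority of cCeLL to FS with margins of 5 and 10 percentage points. FS enters every one of these tests. For agreement, PS does not enter at all.

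The explicit ban therefore leaves out the one result that decides the first test. A reader who knows FS can move an uncertain call toward it without using the image. Agreement then rises for a reason unrelated to the device. The non-inferiority comparisons also lean toward success when cCeLL is truly worse, because the observed gap shrinks. An unmasked read cannot be undone at analysis, so the rule has to be settled before the reads are made.

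**Working it through.** **Step 1: can the stated rule be followed while FS is known?**

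- Scope of the ban: PS only, in both places where it is stated.
- Order: capture precedes frozen sectioning; nothing orders interpretation against the FS report. The sequence of items in Section 6.2 does not settle this either way. FS collection (item 6) is listed before reading (item 8), but de-identification (item 9) is listed after reading, so the list is not a strict chronology.
- People: Section 6.7 has the site pathologist read; FS is reported by the site's pathology department. The available text does not bar one person from doing both for the same sample.
- De-identification: hides labels from the reader, but does not prohibit access to FS or exclude recognition of a case.

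So a site could comply with item 8 to the letter while the reader knows FS.

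**Step 2: the plan's own figure.** Section 8.3.1 says that with true agreement 86% and n = 250, the estimate exceeds 80% with probability above 90%. For X ~ Binomial(250, 0.86), P(X ≥ 201) = 99.4%. The statement reproduces. It concerns the estimate, not passing the test.

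**Step 3: illustration of direction for agreement.** The plan names the exact binomial test with null 80%. I assume one-sided 2.5%. The smallest r with P(X ≥ r | 250, 0.80) ≤ 0.025 is r = 213 (85.2%), with actual size 2.1%.

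Let a fraction c of reads copy FS, whatever the image shows. Apparent agreement is p' = p + (1 − p)c. At p = 0.80:

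- c = 0.05: p' = 0.80 + 0.20 × 0.05 = 0.81
- c = 0.10: p' = 0.80 + 0.20 × 0.10 = 0.82

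| True agreement | c = 0 | c = 5% | c = 10% |
|---|---|---|---|
| 78%, P(X ≥ 213) | 0.3% | 0.9% | 2.5% |
| 80%, P(X ≥ 213) | 2.1% | 5.0% | 10.7% |
| 80%, one-sided 5% instead (r = 211) | 4.5% | 9.6% | 18.3% |

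**Step 4: the same for non-inferiority, at the margin.** I take reads as independent given truth, so the discordant cells are pF(1 − pC) and (1 − pF)pC, each multiplied by (1 − c). Success means (f − g)/n + 1.96·√(f + g)/n below the margin, where f and g are the discordant counts. The value 1.96 follows the 97.5% bound that Section 8.3.1 describes in words; its formula prints z with subscript 0.05.

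- Sensitivity, n = 200, FS 0.90, cCeLL 0.85: cells 0.90 × 0.15 = 0.135 and 0.10 × 0.85 = 0.085, difference 0.05. With c = 10% the difference becomes 0.9 × 0.05 = 0.045. False success goes from 2.7% to 3.9%.
- Specificity, n = 50, FS 0.90, cCeLL 0.80: cells 0.90 × 0.20 = 0.18 and 0.10 × 0.80 = 0.08, difference 0.10, becoming 0.09. False success goes from 3.5% to 5.0%.

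At c = 10%, copying moves agreement by 2 points but the sensitivity difference by 0.5 and the specificity difference by 1. The effect is smaller for the non-inferiority tests, and their starting rates are above 2.5% without any copying.

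**The case against.** The strongest reply is that the study already blinds its reader and only the wording is loose. Section 6.7 names all three modalities and then calls the cCeLL assessments blinded, so a natural reading is that the reader is blinded to both of the others. Images go to a central core, and Sections 6.2 and 8.1 speak of one pathologist. A single central reader would not routinely hold the FS reports of four hospitals. De-identified images also give no stated route to look up an FS result.

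Much of this stands. These provisions lower the chance of exposure, and the general blinding language points toward masking FS. But where the protocol spells out what is withheld, it names PS alone, twice. No available text says that the central core reads the images, and Section 6.7 assigns the reads to the site pathologist. De-identification does not help if the reader reported the FS of the same case and recognises it.

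A reader might go further and infer that FS will be visible, that the protocol permits viewing it, or that the same pathologist will report both. The documents do not support that. They describe no such exposure; they only fail to exclude it. The account in Section 3.2 of FS being relayed to the surgeon describes existing practice and says nothing about the cCeLL reader.

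**Conclusion.** The point holds as a gap in the masking rule. The explicit ban omits FS, FS is the comparator in all three primary tests, and nothing in the available text puts the cCeLL read before the FS report or separates the two readers. Any effect would favour success: upward for agreement, and more weakly for non-inferiority when cCeLL is truly inferior.

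The size is not known. The copying fraction and the alpha of the agreement test are my assumptions; so are independent samples and, for non-inferiority, independent errors given truth. The rise from 2.1% to 5.0% or 10.7% shows direction and sensitivity only. It is not an estimate of this trial's error rate, and at a true agreement of 78% the false-success rate stays at or below 2.5% even with 10% copying. The case for changing the text rests on the low cost of the change, not on a demonstrated bias.

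**What to change.** Amend item 8 of Section 6.2 and item 7 of the Synopsis procedure so that both the FS and the PS results for a sample are withheld from its cCeLL reader until that reader's cCeLL interpretation is locked. State that the cCeLL reader of a sample did not report its FS.

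Reconcile the central core (Synopsis and Section 6.2), the site pathologist (Section 6.7) and the single pathologist (Section 8.1), so that it is clear who reads and whether there is one reader overall or one per site.

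The cost is protocol wording, recording the lock of each read, and possibly scheduling limits at a site where the person who reported FS could not also read the cCeLL images. If sites already mask FS, the amendment only writes down what they do.
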